| 11.3 Vital Signs..... | 15 |
| 11.4 Electrocardiogram (ECG) | 15 |
| 12 References | 15 |
| 13 Appendix 1: Data Handling Conventions..... | 16 |
| 13.1 Visit Time Windows | 16 |
| 13.2 Repeated or Unscheduled Assessments of Safety Parameters | 17 |
| 13.3 Missing Date of Study Medication | 17 |
| 13.4 Missing Severity Assessment for Adverse Events..... | 17 |
| 13.5 Missing Relationship to Study Drug for Adverse Events | 17 |
| 13.6 Missing Date Imputation for Adverse Events | 17 |
| 13.7 Missing Date Imputation for Prior or Concomitant Medications..... | 19 |
| 13.8 Missing Date Imputation for last dose date..... | 20 |

| | | |
|------|---|----|
| 13.9 | Character Values of Clinical Laboratory Parameters..... | 20 |
|------|---|----|

LIST OF ABBREVIATIONS

| | |
|----------------|---|
| AE | Adverse Event |
| CTCAE | Common Terminology Criteria for Adverse Events |
| DSMB | Data and Safety Monitoring Board |
| ESA | Erythropoiesis-Stimulating Agent |
| FACT-An | Functional Assessment of Cancer Therapy – Anemia |
| Hb | Hemoglobin |
| HDL | High-Density Lipoprotein |
| IV | Intravenous |
| LDL | Low-Density Lipoprotein |
| MAP | Mean Arterial Pressure |
| MedDRA | Medical Dictionary for Regulatory Activities |
| PCS | Potentially Clinically Significant |
| PEY | Patient-Exposure-Year |
| RBC | Red Blood Cell |
| SAE | Serious Adverse Event |
| SAP | Statistical Analysis Plan |
| TEAE | Treatment Emergent Adverse Event |
| TIBC | Total Iron Binding Capacity |
| TLF | Tables, Listings, and Figures |
| TSAT | Transferrin Saturation |
| UACR | Urine Albumin-to-Creatinine Ratio |
| ULN | Upper Limit of Normal, value provided by the laboratory |

| | |
|--------------|--|
| WHODD | World Health Organization Drug Dictionary |
| WHO | World Health Organization |
| SOC | System Organ Class (used in MedDRA dictionary) |

1 INTRODUCTION

This statistical analysis plan (SAP) provides a more technical and detailed elaboration of the statistical analyses of efficacy and safety as outlined and/or specified in the final study protocol. Specifications of tables, data listings, and figures (TLF) are contained in a separate document.

2 STUDY OBJECTIVES

The primary objectives of this study are to:

- Evaluate the long-term efficacy and safety of roxadustat in the maintenance of Hb in dialysis and non-dialysis CKD subjects.

The secondary objectives in this study are to:

- Evaluate roxadustat doses and dose adjustments.

The exploratory objectives in this study are to:

- Assess the effect of roxadustat on iron utilization parameters;
- Assess the effect of roxadustat on select biomarkers.

3 STUDY DESIGN

This is an open-label, long-term maintenance study of roxadustat anemia therapy in dialysis and non-dialysis subjects with CKD who completed the treatment period of a Phase 2 roxadustat anemia study in the U.S.

Subjects who received roxadustat in a previous study continued to receive roxadustat at the same dose and frequency as they received at the end of the treatment period in their previous study, unless a dose adjustment was required, at time of switching over to this study. Roxadustat was supplied in an open-label manner to all subjects.

This study (amendment 2) accommodated the potential for prior study participants on a placebo, to switch to this study: Subjects who received placebo in their previous study could start treatment with roxadustat at starting doses according to their weight (Appendix B of the protocol). Planned total study duration was up to 312 weeks (6 years), including up to an additional 1 year under Amendment 2.

Study visits were scheduled every 2 weeks, for the first 104 weeks (2 years) of study drug treatment (time on the previous Phase 2 studies of roxadustat), followed by every 4 weeks until the end of the treatment period.

After the end of treatment (defined as the last day a subject receives study drug) the subjects returned for a follow-up visit 4 weeks later.

The baseline Hb value for efficacy analysis is defined as the mean of the central laboratory Hb value from the baseline visit at Day 1 (prior to receiving the first dose of study drug in this study), plus any other central lab Hb values within 15 days prior to Day 1.

Safety is assessed by vital signs, physical examinations, clinical laboratory values (serum chemistries including liver function tests [LFTs] and complete blood counts [CBC]), electrocardiograms (ECGs), AEs and concomitant medication reporting. Clinical laboratory tests, including LFTs and Hb levels, could y be assessed at additional times on unscheduled visits for safety reasons.

Fifteen subjects entered this study: 1 subject from FGCL-4592-040 and 14 subjects from FGCL-4592-041. All subjects received Roxadustat prior to entering this study (0 subject received placebo). Descriptive analyses will be performed for all subjects.

4 STUDY ENDPOINTS AND ASSESSMENTS

4.1 EFFICACY ENDPOINT

The efficacy endpoints in this study are:

- Mean Hb over selected time periods
- Number (%) of subjects maintaining mean Hb at ≥ 10 g/dL at selected time periods
- Rescue therapy events (composite of transfusions, IV iron, ESAs) and individual rescue therapy modalities
- Roxadustat average weekly doses over selected time periods
- Dose adjustment frequencies (increase, decrease, dose hold, separately)
- Oral iron dose

4.2 SAFETY ASSESSMENTS

Safety assessments include the following:

- Number (%) of subjects with AEs, serious adverse events (SAEs), and clinically significant changes in laboratory values from baseline observations
- Changes from baseline observations in vital signs and ECG findings, and clinical laboratory values, including Total Cholesterol, LDL cholesterol, LDL/HDL ratio, non-HDL cholesterol, HDL cholesterol TSAT, and Ferritin

4.3 SELECT ADDITIONAL LABS OF INTEREST

Exploratory assessments in this study will evaluate the following parameters:

- Reticulocyte hemoglobin content (CHr)
- Highly sensitive C-reactive protein (hs-CRP)
- Hepcidin levels in serum
- eGFR

5 GENERAL STATISTICAL CONSIDERATIONS

5.1 SAMPLE SIZE DETERMINATION

This is an open-label, long-term maintenance study of roxadustat anemia therapy in dialysis and non-dialysis CKD subjects who have completed the treatment period of a phase 2 roxadustat anemia study in the U.S. The study allowed up to 50 non-dialysis, HD, and PD subjects, from up to 20 study centers throughout the U.S.

No power analysis was used to determine the sample size. Analysis Populations

All subjects entered into this study are included for the statistical analyses.

5.2 METHODOLOGY AND CONVENTIONS

Descriptive summary statistics as well as 95% CI for the estimate, if applicable, are provided.

Continuous variables are presented by descriptive statistics: n, mean, standard deviation, median, 25th and 75th percentile, minimum, and maximum. Categorical variables are presented by frequency count and percentage.

Lab results obtained from a central laboratory were used for all analyses. Local laboratory values, if collected in the CRF's, were not recorded.

All confidence intervals are two-sided 95% confidence intervals. All analyses performed use SAS[®] Version 9.3 or higher.

5.3 ADDITIONAL DATA HANDLING RULES AND PRESENTATION SPECIFICATIONS

The following general guidelines apply to all statistical analyses and data presentations:

- The baseline Hb value for efficacy analysis is defined as the mean of the central laboratory Hb value from the baseline visit at Day 1 (prior to receiving the first dose of study drug in this study), plus any other central lab Hb values within 15 days prior to Day 1
- Baseline of other assessments is defined as the last available value obtained prior to the first dose of study drug in this study, unless otherwise specified in this SAP.
- Analysis visits (instead of the nominal visits from CRF) derived from visit dates and visit time windows are used in all analyses, tables, listings and figures. Unscheduled visits within an allowable window are grouped into the closest scheduled visits based on the visit window specified in Appendix 1. For subjects who have more than one measurement at a scheduled visit, the last measurement issued, with the exception of CPK, WBC, liver function tests (i.e., ALT, AST, GGT, ALP, and total bilirubin), in which the maximum measurement issued.
- By default, US conventional units are used for laboratory value presentations. A set of lab summary tables in SI units are also provided based on TLF index.
- Age is calculated as of date that the informed consent form was signed.
 - age = INTCK('YEAR', Birth Date, Date of Informed Consent, 'C')where INTCK is a SAS function.
- Body weight, height and temperatures are converted using the following formula:
 - kg = lb/2.2
 - cm = 2.54 x in
 - C° = (5/9) x (F° – 32)
- For continuous variables that are recorded as “<X” or “>X”, the value of “X” issued in the calculation of summary statistics.
- The mean, standard deviation and median is presented with adding one more decimal to raw data with rounding off. The minimum and maximum is presented with the same number of decimals as in the raw data.
- All percentages are rounded to one decimal place and lined up by the decimal place. The percentage is suppressed when the count is zero.
- Any p-values are rounded to four decimal places and presented as ‘<.0001’ if they are less than 0.0001 before rounding.
- All tables and listings have a header showing “FibroGen, Inc.”, the protocol number, date of the database transfer, and Page x of y. A footer shows the program file path/name, output file path/name, run date and run time.
- Additional data handling conventions are detailed in Appendix 1.

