11.2 CLINICAL LABORATORY PARAMETERS

Descriptive statistics for the following laboratory values and changes from baseline at selected time points are presented to include (but not limited) to the following:

Hematology: Hemoglobin, hematocrit, RBC count, CHr, MCV, WBC count, WBC differential, and platelet counts;

Chemistry: Alkaline phosphatase, ALT, AST, total bilirubin, TSAT, ferritin, total cholesterol, LDL cholesterol, HDL cholesterol, LDL/HDL ratio, CPK, LDH, total protein, albumin, fasting glucose, phosphate, uric acid, BUN, creatinine, sodium, and potassium; HbA1C;

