13 APPENDIX 1: DATA HANDLING CONVENTIONS**13.1 VISIT TIME WINDOWS**

| Endpoint | Visits during Treatment Period | | | | |
|---|--------------------------------|-----------------------------|----------------------|---|------------------------------------|
| | Every 4 weeks ^a | Every 24 weeks ^b | Target Day | Analysis Visit Windows Actual Assessment Day ⁺ | Analysis Visit ⁺⁺ |
| | | | Day 1 | Day 1 | Baseline |
| BP, HR, respiratory rate* | X | | Day 7 * (Week #) + 1 | Target Day plus or minus half the duration to the next Target Day | Weeks 4, 8, 12 then every 12 weeks |
| 12-lead ECG | | X | Day 7 * (Week #) + 1 | [Target Day – 84, Target Day + 83] | Week 24, 48, ... |
| Hb, reticulocyte count, CHr* | X | | Day 7 * (Week #) + 1 | Target Day plus or minus half the duration to the next Target Day | Weeks 4, 8, 12 then every 12 weeks |
| CBC with WBC differential * | X | | Day 7 * (Week #) + 1 | Target Day plus or minus half the duration to the next Target Day | Weeks 4, 8, 12 then every 12 weeks |
| Fasting serum chemistry (including LFTs, lipid panel, glucose) | X | | Day 7 * (Week #) + 1 | Target Day plus or minus half the duration to the next Target Day | Weeks 4, 8, 12 then every 12 weeks |
| Serum iron, ferritin, transferrin (or TIBC), TSAT | X | | Day 7 * (Week #) + 1 | Target Day plus or minus half the duration to the next Target Day | Weeks 4, 8, 12 then every 12 weeks |
| Special labs (CHr, hepcidin, hs-CRP, plus exploratory biomarkers) ^l | | X | Day 7 * (Week #) + 1 | [Target Day – 42, Target Day + 41] | Week 24, 48, ... |
| 
Abbreviations: BP = blood pressure; CBC = complete blood count; CHr = reticulocyte hemoglobin content; CRP = C-reactive protein; ECG = electrocardiogram; HR = heart rate; LFT = liver function test; TIBC = total iron binding capacity; TSAT = transferrin saturation; WBC = white blood cell.
 
* Visit weeks are weekly (week 1 to 4), every 2 weeks (week 6 to 24), every 4 weeks afterwards
 
a Visit weeks may include of: Weeks 13, 37, 61, 85, 109, 133, 157, 181, 205, 229, and 253
 
b Visit weeks may include of: Weeks 25, 49, 73, 97, 121, 145, 169, 193, 217 and 241
 
++ Analysis visits are up to the EOT, which is the last day of treatment.
 
Note: The lower bound for the first visit window starts at Day 1.
 | | | | | |

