13.2 REPEATED OR UNSCHEDULED ASSESSMENTS OF SAFETY PARAMETERS

If a patient has repeated assessments prior to switch to this study, the last result prior to switch is used as baseline, except where otherwise specified. If post-baseline assessments are repeated or unscheduled, the last post-baseline assessment within a visit window is used as the study visit assessment for generating summary statistics. However, all post-baseline assessments are used for PCS value determination and all assessments are presented in the data listings.

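### As SAP 5.3 is written, mean change from baseline in liver tests, WBC and CPK sets a window maximum against a single baseline value and is biased upward; SAP 13.2 gives a conflicting rule

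*SAP*

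**What the plan says.** - **Several values at a visit.** SAP 5.3 takes the last measurement, "with the exception of CPK, WBC, liver function tests (i.e., ALT, AST, GGT, ALP, and total bilirubin), in which the maximum measurement issued" (the final word evidently stands for 'is used').
- **What counts as a visit.** SAP 5.3 replaces the nominal CRF visits: analysis visits "derived from visit dates and visit time windows are used in all analyses, tables, listings and figures".
- **Windows.** SAP 13.1 places the analysis visits for chemistry and CBC at "Weeks 4, 8, 12 then every 12 weeks". Each window is "Target Day plus or minus half the duration to the next Target Day".
- **Baseline.** SAP 5.3: "Baseline of other assessments is defined as the last available value obtained prior to the first dose of study drug in this study".
- **Reported statistic.** SAP 11.2: "Descriptive statistics for the following laboratory values and changes from baseline at selected time points are presented". The list names WBC, alkaline phosphatase, ALT, AST, total bilirubin and CPK. GGT is not named, but the list is stated not to be exhaustive.
- **Competing rule.** SAP 13.2, on repeated or unscheduled safety assessments: "the last post-baseline assessment within a visit window is used as the study visit assessment for generating summary statistics". It makes no exception for liver tests, WBC or CPK.

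**The concern.** If a window holds one value, its maximum is that value and the comparison with baseline is fair. If it holds two or more, the maximum exceeds a typical single value by chance alone, and the mean change inherits that excess. The number of values per window also changes during the study, so the excess changes too. A table by visit can then show a trend that comes only from how many samples fell in each window.

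Long-term safety is part of the primary objective, and liver function has its own monitoring plan (Protocol 4.5.1). The study has 15 subjects, all previously on roxadustat (SAP 3), and no control group (Protocol 4.1.1). No comparison arm would show the same artefact and so expose it.

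**Working it through.** The documents give no expected laboratory change and no within-subject SD, so there is no figure of the plan's own to reproduce. Results are in within-subject SD units, or over an assumed range of CV.

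**Step 1: scheduled liver values per window.** Inputs: chemistry every 4 weeks (Protocol 7.1.1.1.3 and Appendix A); target day = 7 × week + 1 (SAP 13.1); window boundaries at midpoints between target days.

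| Analysis visit | Target day | Window (days) | Scheduled chemistry weeks inside | k |
|---|---|---|---|---|
| Week 4 | 29 | 1–42 | 4 | 1 |
| Week 8 | 57 | 43–70 | 8 | 1 |
| Week 12 | 85 | 71–126 | 12, 16 | 2 |
| Week 24 | 169 | 127–210 | 20, 24, 28 | 3 |
| Week 36 and later | 253, … | 84 days each | three | 3 |

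Taken literally, half the distance to the next target is 42 days on both sides at Week 12. That window then starts at Day 43, overlaps the Week 8 window and holds 3 values (Weeks 8, 12, 16). On that reading the whole step falls between Weeks 8 and 12.

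**Step 2: expected false rise with no true change.** For k independent normal values with SD σ, the expected maximum exceeds the mean by e(k)·σ, where e(k) = ∫ x·k·φ(x)·Φ(x)^(k−1) dx. Baseline is one value with expectation equal to the mean, so the expected change is e(k)·σ. If values in a window share correlation ρ, it becomes e(k)·√(1−ρ)·σ.

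| k | ρ = 0 | ρ = 0.5 (assumed) |
|---|---|---|
| 1 | 0 | 0 |
| 2 | 0.564 | 0.564 × 0.707 = 0.40 |
| 3 | 0.846 | 0.846 × 0.707 = 0.60 |
| 6 | 1.267 | 1.267 × 0.707 = 0.90 |

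As a percentage of the subject's mean, with independent lognormal values and assumed within-subject CVs of 10, 20 and 30%: k = 2 gives about +5.6, +11.1 and +16.4%; k = 3 gives about +8.6, +17.3 and +25.9%.

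**Step 3: effect on a 95% confidence interval, if one is shown.** This comes from 40,000 simulated trials with no true change. The change is the maximum of k values minus one independent baseline value, with a t-interval. The share of intervals wholly above zero (nominal 2.5%) is:

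| k | n = 15, ρ = 0 | n = 15, ρ = 0.5 | n = 10, ρ = 0 | n = 10, ρ = 0.5 |
|---|---|---|---|---|
| 2 | 35% | 18% | 23% | 13% |
| 3 | 69% | about 37% | 47% | 24% |

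With the last of three values at n = 15 and independent values, the mean change is 0.00 SD and the interval excludes zero on either side in 5.1% of trials, as it should.

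**Step 4: WBC.** WBC comes with every CBC, so k depends on the visit schedule, and the documents give three. Counts use midpoint windows.

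| Schedule | Week 4 | Week 8 | Week 12 | Week 24 | Later |
|---|---|---|---|---|---|
| 4-weekly (Protocol Synopsis) | 1 | 1 | 2 | 3 | 3 |
| 2-weekly to 104 weeks including prior study (Protocol 4.1), assuming about 20 weeks of prior treatment | 2 | 2 | 4 | 6 | 6 to Week 72, 5 at Week 84, then 3 |
| SAP 13.1 footnote | 4 | 2 | 4 | 5 | 3 |

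Under the last two schedules the bias is already present at Week 4 and later falls. With independent values it drops from 1.27 SD at k = 6 to 0.85 SD at k = 3 on the 2-weekly schedule.

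**Step 5: CPK.** The same rule and bias apply, but CPK is not among the chemistry analytes listed in Protocol 7.5.1, so its values per window cannot be counted.

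**The case against.** The strongest reply is SAP 13.2. It deals specifically with repeated safety assessments and takes the last value for summary statistics; if it governs, the bias from scheduled values is zero. This stands in part. A reader might infer that the SAP is certain to report false rises, and the documents do not support that, because the two rules conflict and nothing ranks them. Yet SAP 5.3 names these analytes as an explicit exception and covers all analyses, so a general default does not plainly cancel it. Nor is the last value entirely neutral. Protocol 4.5.1 has abnormal liver tests repeated until they stabilise or normalise, so the last value in a window would favour resolved results.

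A second reply is that the maximum applies only to several measurements at one scheduled visit, and chemistry visits are 4-weekly. On that reading the liver bias comes only from repeats. But SAP 5.3 has already replaced nominal visits with windows in every output, and those repeats are triggered by high values, so the maximum would still lean upward, though only occasionally.

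Third, a confidence interval for these tables is not clearly planned. SAP 5.2 gives intervals only where applicable, and Protocol 10.6 ties them to efficacy endpoints. The interval percentages are therefore conditional.

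Two further inferences go too far. One is a single step after Week 12: the liver step begins at Week 12, and the WBC pattern depends on the schedule. The other is that a real signal could not be recognised at all: SAP 13.2 uses every post-baseline value to determine potentially clinically significant (PCS) results and lists them all, and Protocol 10.6.4 flags out-of-range values. That also means the maximum is not needed in the mean-change tables to protect safety.

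**Conclusion.** The concern holds for SAP 5.3 as written. With midpoint windows and 4-weekly chemistry, mean change in the liver tests would carry a false rise of about +0.56 SD at Week 12 and +0.85 SD from Week 24 if values are independent, or about +0.40 and +0.60 SD at a correlation of 0.5. The percentage rises and the correlation are assumptions, because the documents give no within-subject variability. The interval figures also assume that 15 (or 10) subjects contribute to the window. The direction of the bias does not depend on these choices; its size and timing do. Whether it reaches the report depends on which of SAP 5.3 and 13.2 is applied. Severity is moderate: the tables are descriptive, and individual abnormal values are captured elsewhere.

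**What to change.** In SAP 5.3, 11.2 and 13.2, state one rule. For descriptive statistics and change from baseline, every analyte contributes one value per window, chosen without regard to its size: the scheduled value nearest the target day. Make 5.3 and 13.2 agree on this. Use the maximum only in a separate table of worst post-baseline or PCS values, with no mean change from baseline attached. In SAP 13.1, give explicit, non-overlapping day ranges, in particular for Week 12, and state which visit schedule was followed.

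The cost is SAP wording, one extra derivation and one extra table. No new data are needed.

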6 SUBJECT ACCOUNTABILITY AND DISPOSITION

Number and percent of subjects are summarized by discontinuation reason.

7 DEMOGRAPHICS AND OTHER BASELINE CHARACTERISTICS

Demographic parameters and important baseline and disease characteristics are summarized. These include but may not be limited to age and age group, sex, ethnicity, race, weight, body-mass index (BMI), Hemoglobin, Ferritin and Ferritin group (≤ 100 vs. > 100 ng/mL), TSAT and TSAT group ($\leq 20\%$ vs. $> 20\%$), iron repletion status ([TSAT $\geq 20\%$ and ferritin ≥ 100 ng/mL] vs. other), baseline C-reactive protein (CRP) group (CRP \leq ULN vs. CRP $>$ ULN), eGFR and eGFR group (< 10 , 10 - < 15 , 15 - < 30 , 30 - < 45 , 45 - < 60 , and ≥ 60 mL/min/1.73m²).

8 STUDY MEDICATION

8.1 EXTENT OF EXPOSURE AND DOSE ADMINISTRATION

Treatment duration, the Patient-Exposure-Year (PEY) are defined as (Last Dose Date – First Dose Date + 1)/365.25, during this study.

Average weekly study dose (in mg or mg/kg) are summarized for selected time periods such as every 4 weeks, from week 0 – 24, every 8 weeks, from week 25-48, and every 12 weeks, starting week 49 through EOT/ET.

Dose adjustment frequencies (number (%)) of subjects with a dose increase, dose decrease, dose hold, separately)

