2.2. Secondary Objectives

Evaluate roxadustat doses and dose adjustments.

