3. ENDPOINTS AND ASSESSMENTS

3.1. Efficacy

The efficacy endpoints in this study are:

- Mean monthly Hb values over time;
- Number (%) of subjects maintaining monthly (monthly defined as a 4-week interval) mean Hb at ≥ 10 g/dL during study participation upon correction (correction is defined as having achieved 2 consecutive Hb values of ≥ 10 g/dL);
- Number (%) of subjects maintaining Hb between 10-13 g/dL for at least 60% of scheduled Hb assessments after the first Hb value is 10 g/dL or higher.
- Composite rate of summarized rescue therapy events (transfusions, IV iron, ESAs) and rate of individual rescue therapy events;
- Number (%) of subjects with phlebotomies;
- Roxadustat weekly total doses over time;
- Dose adjustment frequencies;
- Hb variability;
- Number (%) of subjects withdrawn from the study due to inadequate efficacy.

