10.6.2. Efficacy Analyses

Hemoglobin results obtained from the central laboratory will be used for all efficacy analyses.

Baseline Hb value for efficacy analysis is defined as the mean of the central laboratory Hb value from the Baseline Visit Day 1 (prior to receiving the first dose of study drug in this study), plus any other central laboratory Hb values obtained within 15 days prior to Day 1. Baseline eGFR, ferritin, TSAT, and other efficacy endpoints are defined as the last value prior to the first dose of study treatment.

All efficacy analyses will be based on the EE population.

- Monthly mean Hb values and changes from baseline will be summarized descriptively for the Dialysis, Non-Dialysis, and Newly Initiated populations at each scheduled time point as well as monthly
- The number (%) of subjects maintaining Hb ≥ 10 g/dL during study participation, the composite rate of summarized rescue therapy events (transfusions, IV iron, ESAs) and rate of individual rescue therapy events, and the number (%) of subjects receiving phlebotomies will be summarized for the Dialysis, Non Dialysis and Newly Initiated populations
- The dose level at the time of Hb response will be summarized descriptively
- The frequency of dose increases and decreases and use of rescue therapy will also be tabulated. Median time to Hb response will be estimated for each subject previously receiving placebo (Newly Initiated group) using the Kaplan-Meier method. Hemoglobin response is defined as a Hb increase from baseline of at least 1.0 g/dL. In addition, median initial responsive time and dose will be tabulated to evaluate when an initial Hb change from baseline reaches at least 1.0 g/dL. Number (%) of

subjects, scheduled Hb values, and consecutive Hb values achieved for a variety of Hb ranges between 11.0 and 13.0 g/dL, as well as above or below these ranges, during 4-week study intervals throughout the treatment period will be tabulated.

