APPENDIX C. DOSE ADJUSTMENT GUIDELINES FOR ROXADUSTAT

All dose adjustments should be based on Hb values using a point-of-care device, such as HemoCue® or CritLine®. In the event that the central lab Hb value of the site visit is significantly different and the dose adjustment decision based on the HemoCue® / CritLine® value is being re-considered, the Medical Monitor should be contacted, if possible.

Dose adjustment reviews will occur on Week 4, and at intervals of every 4 weeks thereafter (Weeks 8, 12, 16, etc.), except in the event of excessive hematopoiesis, in which case doses may be adjusted at any time. In such cases, dose adjustment reviews are resumed at 4-week intervals. For example, if the subject's Hb increases > 2.0 g/dL from Week 1 to Week 3, the subject's dose is reduced by one dose step at Week 3. The next dose adjustment review should occur 4 weeks later at Week 7. If the dose adjustment interval falls on a non-study visit week (starting Week 4), the dose adjustment review should be performed at the next scheduled study visit if a dose adjustment was not required at the previous visit. For example, if a subject's visit is scheduled for Weeks 6 and 8, and the dose adjustment would occur at Week 7, then the dose adjustment should be evaluated at the Week 8 visit.

All subjects will be dosed orally TIW during the Treatment period. During the course of the study, the dose and the dosing frequency may be changed to optimize efficacy and tolerability based on the clinical judgment of the investigator and study medical monitor. If a subject requires < 20 mg TIW (ie, < 60 mg per week) to maintain the target Hb level, the dosing frequency should be reduced in a step-wise fashion eg, TIW to BIW, BIW to QW, QW to Q-2 Week etc. The Medical Monitor should be notified as soon as possible of such dose change. The maximum roxadustat dose is 3.0 mg/kg per dose or 400 mg (whichever is lower).

The following scenarios are defined as “excessive hematopoiesis”;

Hb increases by > 2.0 g/dL at any time within a 4 week period: reduce the dose by one dose step.

Hb reaches or exceeds 13 g/dL: hold dosing, check Hb weekly. Resume dosing when Hb < 12.0 g/dL (for US subjects central lab Hb value preferred), at a dose that is reduced by two dose steps.

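### SAP 8.1 reports dose-adjustment frequency only as the number (%) of subjects adjusted, with no period, event count or exposure denominator, so it cannot show how often doses change

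*SAP*

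**What the plan says.** The secondary objective in Protocol 2.2, repeated in SAP Section 2, is to "Evaluate roxadustat doses and dose adjustments". Protocol 3.1 lists "Dose adjustment frequencies" as an efficacy endpoint without a unit. Protocol 10.6.2 adds: "The frequency of dose increases and decreases and use of rescue therapy will also be tabulated".

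SAP 4.1 carries the endpoint forward and splits it into increases, decreases and holds. SAP 8.1 is the only place that says what will be computed: the number (%) "of subjects with a dose increase, dose decrease, dose hold, separately". It is a fragment without a verb. It states no observation period, no count of adjustments and no exposure denominator. SAP 10.1, which sets out the efficacy analyses, does not mention dose adjustments.

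Three neighbouring provisions matter:

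- SAP 8.1 defines PEY and summarises average weekly dose in 4-, 8- and then 12-week periods.
- SAP 10.1 analyses rescue therapy as events over total PEY.
- SAP 11.1 gives adverse event rates per 100 PEY.

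**The concern.** A count of subjects with a given type of change answers whether a change occurred, not how often. In a study planned for up to 312 weeks, with a dose review every 4 weeks, these are different questions. A subject titrated once and then stable cannot be told apart from one whose dose moves up and down for years.

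If the count is cumulative over the study, it also rises with time on treatment. Subjects may withdraw at any time (Protocol Section 8) and are not replaced (Protocol 10.5), so a single percentage can pool short and long follow-up. At stake is the dose-adjustment part of the secondary objective: the reported figure could look the same for a stable and an unstable dosing course.

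**Working it through.** The plan states no expected adjustment rate, power or precision, so there is no figure of its own to reproduce. The check asks what the SAP 8.1 measure would show under a range of assumed rates.

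**Inputs from the documents**

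- Opportunities to adjust (Protocol Appendix C): "Dose adjustment reviews will occur on Week 4, and at intervals of every 4 weeks thereafter". That is 52/4 = 13 reviews a year, 65 in 260 weeks and 78 in 312 weeks.
- Planned maximum duration (SAP Section 3): 312 weeks.
- Sample (SAP Section 3): "Fifteen subjects entered this study". One subject is 1/15 = 6.7 percentage points.

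**Assumed input:** p, the chance of a given type of change at one review, taken as constant and independent across reviews.

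**Cumulative subject count.** The chance of at least one change in k reviews is 1 − (1 − p)^k. For example, with p = 5%: 1 − 0.95^13 = 48.7% and 1 − 0.95^65 = 96.4%.

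| p per review | Changes per year (13p) | 52 wk | 104 wk | 260 wk | 312 wk |
|---|---|---|---|---|---|
| 1% | 0.13 | 12% | 23% | 48% | 54% |
| 2% | 0.26 | 23% | 41% | 73% | 79% |
| 5% | 0.65 | 49% | 74% | 96% | 98% |
| 10% | 1.3 | 75% | 94% | 99.9% | 100% |
| 20% | 2.6 | 95% | 99.7% | 100% | 100% |

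Three results follow.

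- *Loss of discrimination.* At 260 weeks, p = 5% and p = 10% differ twofold in frequency (0.65 against 1.3 a year), but the percentages differ by 99.9 − 96.4 = 3.5 points, less than one subject in 15. At 312 weeks, p = 5%, 10% and 20% mean 78p = 3.9, 7.8 and 15.6 changes per subject, yet the expected counts are 14.7, 15.0 and 15.0 of 15.
- *Dependence on follow-up.* With the same p = 5%, a subject followed for 1 year has a 49% chance of being counted and one followed for 5 years has 96%.
- *No saturation for rare types.* At p = 1% the figure reaches only 54% at 312 weeks.

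**Unequal subjects.** If rates vary strongly between subjects (gamma with shape 1), the chance is 1 − 1/(1 + λT). At T = 6 years this gives 1 − 1/7 = 86%, 1 − 1/13 = 92% and 1 − 1/25 = 96% for λ = 1, 2 and 4 a year. The approach to 100% is slower, but a fourfold difference in rate still spans only 10 points.

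**If n (%) were tabulated by period instead.** A 12-week period holds 3 reviews: 1 − 0.95^3 = 14.3%, 1 − 0.90^3 = 27.1% and 1 − 0.80^3 = 48.8%. These do not saturate and they do track p.

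**Events per PEY.** Exact Poisson 95% intervals, assuming all 15 subjects are followed throughout and events are independent:

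| True rate per year | 6 years each (90 PEY) | One study year (15 PEY) | Subject count at 6 years |
|---|---|---|---|
| 1 | 0.80–1.23 | 0.56–1.65 | 99.8% |
| 2 | 1.72–2.31 | 1.35–2.86 | 100.0% |
| 4 | 3.60–4.44 | 3.05–5.15 | 100.0% |

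Over the whole study the rate separates courses that the subject count cannot. Within one study year, the intervals for 1 and 2 a year overlap.

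**The case against.** Four points can be made for the plan.

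- *The period is unstated, not stated as the whole study.* The fragment directly follows a dose summary given by period, and SAP Section 1 places table specifications in a separate document. If n (%) is tabulated by those periods, most of the saturation argument falls away, as shown above. This stands: the cumulative reading is an inference. It does not rescue the text, because no period is given and a per-period subject count still omits repeat changes within a period.
- *Frequency need not mean a rate.* A reader might infer that the SAP departs from what the protocol required. The documents do not support that. The protocol gives no unit; its Section 10.6.4 uses frequency counts for the number (%) of subjects with adverse events, and SAP 5.2 presents categorical variables by count and percentage. A subject count is a permissible reading, though not an informative one.
- *The table might not saturate.* A reader might infer that nearly every subject will show every type of change. The documents give no adjustment rate and do not show that holds are common, so this cannot be asserted.
- *The objective is partly served elsewhere.* Weekly dose by period, and the plot of mean Hb with mean weekly dose in SAP 10.1, address dose level. It would be wrong to say the secondary objective goes unanswered. But rises and falls cancel in a mean, so these summaries do not show how many changes were made.

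**Conclusion.** The point holds in a limited form. As written, SAP 8.1 cannot show how often doses change at any adjustment rate; this follows from counting subjects and needs no assumption. The dependence on follow-up holds if the count is cumulative over the study, which is the natural reading when no period is given but is not stated.

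Saturation is conditional. It applies to types of change occurring at roughly 5% or more of 4-weekly reviews over 5 to 6 years, with similar and constant chances across subjects. It does not apply at about 1%. The 312 weeks is a planned maximum and the actual exposure of the 15 subjects is not reported, so neither the degree of saturation nor the mix of follow-up times can be fixed from the documents.

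The study is descriptive and no test or error rate is affected. The change is still worth making, because the SAP already uses PEY rates for rescue therapy and adverse events and defines PEY in the same section.

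**What to change.** In SAP 8.1:

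1. Make the main dose-adjustment result the number of increases, decreases and holds, each divided by total PEY as already defined, with a 95% CI, overall and by study year.
2. State the counting rule, for example whether a hold followed by a restart at a lower dose counts once or twice, and whether a change of dosing frequency counts.
3. State the interval method. A simple Poisson interval will be too narrow if rates differ between subjects, so allow for that variation or show the distribution of counts per subject beside the rate.
4. Keep number (%) of subjects as a supplement and name its period.

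The cost is one extra descriptive table from dosing data and exposure already derived. With 15 subjects the rates by study year will be imprecise: at 15 PEY, a rate of 1 a year carries an interval of 0.56–1.65, and later years will be wider if subjects have left.
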